7.2.5 Safety analyses

Adverse events will be coded using the current version of Medical Dictionary for Regulatory Activities (MedDRA) coding dictionary. Standard BI summary tables and listings will be produced.

[figure not shown]
All randomised and treated patients will be included in the safety analysis. In general, safety analyses will be descriptive in nature and will be based on BI standards. No hypothesis testing is planned. Statistical analysis and reporting of adverse events will concentrate on treatment-emergent adverse events (TEAE). To this end, all adverse events occurring between start of treatment and end of the residual effect period will be considered 'treatment-emergent'; the residual effect period (REP) is defined as 16 weeks after the last dose of trial medication. Adverse events that start before first drug intake and deteriorate under treatment will also be considered as 'treatment-emergent'.

Frequency, severity, and causal relationship of adverse events will be tabulated by system organ class (SOC) and preferred term after coding according to the current version of the MedDRA at database lock.

Laboratory data will be analysed both quantitatively as well as qualitatively. The latter will be done via comparison of laboratory data to their reference ranges. Values outside the reference range as well as values defined as clinically relevant will be highlighted in the listings. Treatment groups will be compared descriptively with regard to distribution parameters as well as with regard to frequency and percentage of patients with abnormal values or clinically relevant abnormal values.

Vital signs, physical examinations, or other safety-relevant data observed at screening, baseline, during the course of the trial and at the end-of-trial evaluation will be assessed with regard to possible changes compared to findings before start of treatment.

Immunogenicity data will be analysed in a descriptive way.

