6. GENERAL ANALYSIS DEFINITIONS

6.1 TREATMENTS

For more details of study information on the treatment to be administered, assignment to treatment, and selection of dose, refer to Section 4 of the CTP.

The following study phases are defined:

Table 6.1: 1 Flow chart of analysis phases

Study analysis phase	Description	Start (included)	End (included)
Screening phase	Screening	Earliest of (Date of informed consent, first screening procedure)	Date/time of start of the first study dose minus 1 minute.
Loading treatment phase	On-treatment period	Date/time of start of the first study loading dose (Day 1)	Earlier of: i) Date/time of start of the first maintenance dose; or, ii) Date of end of last loading dose + 112 days at 11:59 p.m. if patient early discontinued study treatment before the first maintenance dose
Maintenance treatment phase (primary analysis at week 16)		Date/time of start of the first study maintenance dose (if applicable)	Earlier of: i) Date/time of start of the first maintenance dose at or after week 16; or, ii) Date of end of last maintenance dose + 112 days at 11:59 p.m. if patient early discontinued study treatment before week 16
Maintenance treatment phase (post primary analysis at week 16)		Date/time of start of the first maintenance dose at or after week 16 (if applicable)	Earlier of: i) Date/time of start of first dose in OLE 1368.24 trial; or, ii) Date of end of last study maintenance dose + 112 days at 11:59 p.m.
Follow-up ¹ phase (if applicable)	Off-treatment period (if applicable)	Date of end of last study dose + 113 days at 0:00 a.m.	Latest of: i) Date of EOS visit; ii) end date on trial termination page at 11:59 p.m. iii) Date/time of start of first dose in OLE 1368.24 trial;

Dates are defined individually per patient. If more than one date is associated with a specific visit, measurements associated with a specific date are assigned to a study analysis phase according to the rules specified in the table. An analysis phase will not extend beyond the start date of the following phase.

¹ The off-treatment period (i.e. Follow-up phase) only exists if the trial completion date is after the date of end of last administration + 112 days.

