V9	Week 16	Day 113	+/- 7	106	120	100	127
V10	Week 20	Day 141	+/- 7	134	148	128	155
V11	Week 24	Day 169	+/- 7	162	176	156	183
V12	Week 28	Day 197	+/- 7	192	204	184	211
V13	Week 32	Day 225	+/- 7	218	232	212	239
V14	Week 36	Day 253	+/- 7	246	260	240	267
V15	Week 40	Day 281	+/- 7	274	288	268	295
V16 ^C	Week 44	Day 309	+/- 7	302	316	296	323
V17	Week 48	Day 337	+/- 7	330	344	324	351
V18 ^D	Week 52 (EoT)	Day 365	+/- 7	358	372	352	393
V19	Week 60	Day 421	+/- 7	414	428	394	449
V20	Week 68 (EoS)	Day 477	+/- 7	470	484	450	491

For patients who discontinue the treatment early and are not willing to follow the whole visit schedule:

- EoS LD^B+112 - - -

Days are counted relative to the day of first treatment, which is defined as Day 1.

^A Note that measurements made at Day 1 and assigned to the on-treatment period (because mistakenly made after start of infusion of trial treatment) via assessment on date and time (i.e. safety laboratory) will not be assigned to Day 1. Such data will be listed only.

^B LD=Last dose.

^C Data within the extended time window of Week 8/16 but after the actual dose at Week 8/16 will not be selected to represent Week 8/16 except for local tolerability and post-dose vital sign assessments.

^D For the patients who enter OLE trial, the EOT will be the last visit (i.e., V19 and V20 are not required). The EOS (=individual end of the study) will be the first administration of the trial drug in OLE trial.

Repeated and unscheduled efficacy, safety XXXXXXXXXX measurements will be handled similarly to scheduled measurements and will also be assigned to a time window depending upon the date of measurement.

Only one observation per time window will be selected for statistical analysis at a particular visit – the value which is closest to the protocol planned visit day will be selected. If there are two observations which have the same difference in days to the planned day, the later value

will be selected. If there are two observations on the same day, the worst value will be selected.

Note that data within the extended time window of Week 8/16 but after the actual dose at Week 8/16 will not be selected to represent Week 8/16 except for local tolerability and post-dose vital sign assessments.

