7.8 SAFETY ANALYSIS

All safety analyses will be performed following BI standards. No hypothesis testing is planned. OC-IR and OR methods will be used for safety reporting.

In primary analysis, AE and possibly clinically significant laboratory abnormalities up to week 16 will be analyzed. In final analysis, AE and possibly clinically significant laboratory abnormalities up to and post the first maintenance treatment at or after week 16 will be analyzed separately.

Primary analysis: AE and possibly clinically significant laboratory abnormalities up to week 16

The analysis will include all on-treatment events up to the treatment at week 16 based on SAF. If patient early discontinued from treatment prior to week 16 or missed week 16 treatment, then the on-treatment events up to Day 127 (the right limit of the extended week 16 visit window) will be included.

Final analysis: AE and possibly clinically significant laboratory abnormalities prior to the first maintenance at or after week 16

The analysis will include on-treatment events up to the first maintenance treatment at or after week 16 based on SAF. If a patient early discontinued from treatment prior to week 16, then the patient's events up to the end of REP of the last treatment will be included.

One additional group will be reported for AE and possibly clinically significant laboratory abnormalities, which is the combination of Arm 1, 2, 3 and 4 ("Speso Total").

Final analysis: AE and possibly clinically significant laboratory abnormalities post the first maintenance at or after week 16

The analysis will include on-treatment events post the first maintenance treatment at or after week 16 based on SAF-post 16. Only patients who have received at least one dose of treatment at or after week 16 will be included.

For AE and possibly clinically significant laboratory abnormalities, except for 5 treatment arms of the trial, one additional group will be reported which is the combination of Arm 1, 3 and 5 [REDACTED]

As the onset time of an AE will not be collected in the trial, any AE which occurs on the same day as a treatment dose will be assigned to the "post treatment". For safety assessments by visits, if time is not collected, data on the same day of a treatment dose will be treated to be "prior treatment" except for scheduled local tolerability and post-dose vital signs assessments.

Off-treatment data will be listed only

Additional analyses on AE will be also included:

AE within loading stage

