7.8.1 Adverse events

AEs will be coded with the most recent version of MedDRA.

The analyses of AEs will be descriptive in nature. All analyses of AEs will be based on the number of patients with AEs and not on the number of AEs. System organ classes (if applicable) will be sorted according to the standard sort order specified by the EMA, preferred terms (if applicable) will be sorted by total frequency (within system organ class) across all treatment arms, or, if a total column across all arms is not foreseen in the table, by total frequency (within system organ class) across the BI arms.

For details on summarization of AE data, please refer to "Handling and summarization of adverse event data for clinical trial reports and integrated summaries" (7) and "Handling of missing and incomplete AE dates" (4).

The analysis of AEs will be based on the concept of treatment emergent AEs. Since only the start date of an AE is collected (without start time), any AE occurrence on the same day as the first Spesolimab administration will be assigned to the on-treatment phase.

An overall summary of AEs will be presented by treatment. This overall summary will include summary statistics for the class of other significant AEs (sponsor definition based on ICH E3) and for the class of AESIs.

Based on the specification provided in ICH E3 (9), the sponsor has defined AEs which are to be classified as 'other significant'. For the current trial, these will include those non-serious AEs which were reported with 'action taken = Drug withdrawn' or 'action taken = Dose reduced'.

The following is considered an AESI in this trial:

Systemic hypersensitivity reactions including anaphylactic reaction

Severe infections (according to RCTC grading in CTP Appendix 10.2)

Opportunistic and mycobacterium tuberculosis infections

Hepatic injury

The investigator had to classify on the eCRF whether an observed AE was an AESI or not.

In addition, user defined adverse event concepts (UDAEC) identified through specific search criteria will be reported separately (see [Table 7.8.1: 1](#)).

Table 7.8.1: 1 Project MEDDRA search criteria for User Defined Adverse Events Concepts

User Defined AE Concepts	Categories
Infusion/Systemic hypersensitivity reactions including anaphylactic reactions	Narrow SMQ “Anaphylactic reaction” Narrow SMQ “Angioedema” Narrow SMQ “Hypersensitivity”
Opportunistic infections	Narrow SMQ “Opportunistic infections”:

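### Final-analysis AE tables give crude patient percentages over unequal time at risk: early discontinuers count to last dose + 112 days, and OLE entrants stop at their first OLE dose

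*SAP*

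**What the plan says.** **Before Week 16, final analysis (SAP 7.8).** The rule for continuing patients is "The analysis will include on-treatment events up to the first maintenance treatment at or after week 16 based on SAF". For a patient who stopped treatment before Week 16, "events up to the end of REP of the last treatment will be included". Protocol 7.2.5 sets the length: "the residual effect period (REP) is defined as 16 weeks after the last dose of trial medication". SAP Table 6.1: 1 writes this as last dose + 112 days.

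**Before Week 16, primary analysis (SAP 7.8).** If a patient discontinued early or missed the Week 16 treatment, "then the on-treatment events up to Day 127 (the right limit of the extended week 16 visit window) will be included". The loading-stage AE tables are capped in the same way, at Day 71.

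**After Week 16.** Table 6.1: 1 ends the phase at the earlier of last dose + 112 days and "Date/time of start of first dose in OLE 1368.24 trial". Footnote D of Table 6.7: 1 adds: "For the patients who enter OLE trial, the EOT will be the last visit (i.e., V19 and V20 are not required". Patients who do not enter the OLE are followed to Week 68 (Protocol 3.1).

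**Metric.** SAP 7.8.1 states: "All analyses of AEs will be based on the number of patients with AEs and not on the number of AEs". Under SAP 7, percentages use all patients in the analysis set as denominator unless specified otherwise. SAP 7.7 summarises the amount of drug given and names neither duration nor patient-years.

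**The concern.** A crude percentage is comparable between arms only if the arms were observed for similar lengths of time. Here the length depends on whether and when a patient stops treatment, and later on whether the patient enters the OLE.

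Both may depend on response. Rescue therapy for worsening PPP leads to discontinuation of trial treatment (Protocol 3.3.4.1 and 4.2.2.1), and worsening of the underlying disease is itself recorded as an AE (Protocol 5.2.6.1.1). AE tables use original results (SAP 6.6.3), so events after rescue are not removed. An arm with more early discontinuers therefore collects more follow-up in the pre-Week-16 table, some of it after rescue.

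Two things are at stake. One is how the final report's placebo-controlled AE table and its post-Week-16 regimen comparison are read. The other is agreement between the two planned clinical trial reports, which can show different percentages for what looks like the same period.

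**Working it through.** **Inputs.** REP of 112 days (Protocol 7.2.5; SAP Table 6.1: 1). Planned dosing days before Week 16: 1, 8, 15, 22, 29, 57 and 85; Week 16 is Day 113 and Week 52 is Day 365 (flow chart; SAP Table 6.7: 1).

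**Check against the plan's own figure.** End of REP = day of last dose + 112. For a Week 52 last dose, 365 + 112 = 477, which is the planned Week 68 visit day.

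**Pre-Week-16 table.** A continuing patient is cut at Day 113. For early discontinuers:

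| Last dose | Final analysis: end of REP | Ratio to Day 113 | Primary analysis: earlier of REP end and Day 127 |
|---|---|---|---|
| Day 1 | 113 | 1.00 | 113 |
| Week 1 | 120 | 1.06 | 120 |
| Week 2 | 127 | 1.12 | 127 |
| Week 3 | 134 | 1.19 | 127 |
| Week 4 | 141 | 1.25 | 127 |
| Week 8 | 169 | 1.50 | 127 |
| Week 12 | 197 | 1.74 | 127 |

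With the ±7-day visit window, the Week 12 row runs from Day 190 to Day 204. The Day 127 cap limits the ratio to 127/113 = 1.12.

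**Post-Week-16 table.** A completer who does not enter the OLE has 477 − 113 = 364 days. The day of the first OLE dose is not stated, so a range is needed:

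- Day 365: 252 days, 364/252 = 1.44
- Day 393: 280 days, 364/280 = 1.30
- Day 421: 308 days, 364/308 = 1.18

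**Illustrative size (assumptions).** Assume a constant hazard that is equal in all arms, with full observation to the cut-off. If p is the risk over T days, the risk over t days is 1 − (1 − p)^(t/T).

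*Before Week 16, 60% event by Day 113.*

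- Last dose Week 8: 1 − 0.4^(169/113) = 74.6%
- Last dose Week 12: 1 − 0.4^(197/113) = 79.8%
- Effect of 10 points more discontinuation: 0.10 × 14.6 = 1.5 points, or 0.10 × 19.8 = 2.0 points

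*Before Week 16, rarer events, last dose Week 12.* With a 5%, 20% or 50% risk by Day 113, a discontinuer's risk is 8.6%, 32.2% or 70.1%. The arm percentage becomes 5.4%, 21.2% or 52.0% if 10% discontinue, and 6.1%, 23.7% or 56.0% if 30% do.

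*After Week 16, 20% risk over 364 days.* Take 80% OLE entry in one arm and 40% in another (assumption). With the first OLE dose at Day 365, the arms show 15.5% and 17.7% at identical risk. At Day 421 they show 17.8% and 18.9%. For a 50% event the pairs are 40.5% and 45.2% (Day 365), and 45.5% and 47.7% (Day 421).

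**The case against.** The cut-offs themselves can be defended. Counting to the end of the REP follows the protocol's definition of a treatment-emergent event, and stopping at the first OLE dose keeps events on extension drug out of this trial. The two reports differ because one is a Week 16 data cut and the other has full follow-up, and both rules are written out. All of this stands: the plan does not contradict itself, and the REP-based table should remain. Replacing it with a capped table plus a listing would do harm. Early discontinuers are not in SAF-post 16, and the overall-period tables show only Arms 1 to 4, so late events in placebo discontinuers would appear in no by-arm AE table.

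The effect is also small beside the arm sizes. With 20 or 40 patients per arm, one patient is 5 or 2.5 points, and safety is descriptive with no testing. That limits the priority of the point but does not remove it.

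A reader might infer more than the documents support:

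- *That OLE entrants are cut at Week 52.* Week 52 is their last visit; the phase ends at the first OLE dose. The ratio of 1.44 is therefore an upper value.
- *That discontinuers generally run to Day 197.* That needs a last dose at Week 12. It also needs the patient to stay under observation, and consent may be withdrawn at any time.
- *That this is the only placebo-controlled safety comparison.* The primary report already gives one with the Day 127 cap, and the loading-stage tables give another capped at Day 71.
- *That the active drug is made to look safer.* The rules are the same in every arm, and the documents give no discontinuation or OLE entry rates. After Week 16, Arm 5 also receives active drug.
- *That no time-at-risk rate will be produced.* SAP 7.8.1 refers AE summary details to a sponsor guideline that is not available here, and parts of the SAP are removed. Such rates are absent from the visible text only.

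**Conclusion.** The point holds as a cheap improvement, not as an error that threatens the trial's conclusions. The final AE tables mix unequal follow-up: up to 1.74 times the time at risk for a Week 12 discontinuer before Week 16, and up to 1.44 times for a completer outside the OLE compared with an OLE entrant after Week 16. The visible SAP gives no person-time with which a reader could correct for this.

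A distortion between arms arises only if discontinuation or OLE entry differs by arm. Its size is therefore an assumption: about 1.5 to 2 points per 10 points more discontinuation for a 60% event with late last doses, about 0.4 points for a 5% event, and less for earlier last doses. The direction is unknown from the documents.

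**What to change.** 1. In the final pre-Week-16, post-Week-16 and overall AE tables, report total time at risk per arm. Add patients with a first event per 100 patient-years at risk for any TEAE, SAEs, AESIs and the user-defined AE concepts. If the sponsor's AE guideline already supplies these, say so in SAP 7.8.
2. Keep the REP-based pre-Week-16 table that the protocol's TEAE definition calls for. Beside it, show the same table with the primary analysis's Day 127 cap, so that the two reports can be compared directly.
3. Tabulate REP events after Day 127 by arm, placebo included, and do not only list them.

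This uses data already planned for collection and costs some SAP wording and extra table columns. Its limitation is that rates per patient-year assume a roughly constant hazard, so they should accompany the percentages and not replace them.

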7.8.1 Adverse events

AEs will be coded with the most recent version of MedDRA.

The analyses of AEs will be descriptive in nature. All analyses of AEs will be based on the number of patients with AEs and not on the number of AEs. System organ classes (if applicable) will be sorted according to the standard sort order specified by the EMA, preferred terms (if applicable) will be sorted by total frequency (within system organ class) across all treatment arms, or, if a total column across all arms is not foreseen in the table, by total frequency (within system organ class) across the BI arms.

For details on summarization of AE data, please refer to "Handling and summarization of adverse event data for clinical trial reports and integrated summaries" (7) and "Handling of missing and incomplete AE dates" (4).

The analysis of AEs will be based on the concept of treatment emergent AEs. Since only the start date of an AE is collected (without start time), any AE occurrence on the same day as the first Spesolimab administration will be assigned to the on-treatment phase.

An overall summary of AEs will be presented by treatment. This overall summary will include summary statistics for the class of other significant AEs (sponsor definition based on ICH E3) and for the class of AESIs.

Based on the specification provided in ICH E3 (9), the sponsor has defined AEs which are to be classified as 'other significant'. For the current trial, these will include those non-serious AEs which were reported with 'action taken = Drug withdrawn' or 'action taken = Dose reduced'.

The following is considered an AESI in this trial:

Systemic hypersensitivity reactions including anaphylactic reaction

Severe infections (according to RCTC grading in CTP Appendix 10.2)

Opportunistic and mycobacterium tuberculosis infections

Hepatic injury

The investigator had to classify on the eCRF whether an observed AE was an AESI or not.

In addition, user defined adverse event concepts (UDAEC) identified through specific search criteria will be reported separately (see [Table 7.8.1: 1](#)).

Table 7.8.1: 1 Project MEDDRA search criteria for User Defined Adverse Events Concepts

User Defined AE Concepts	Categories
Infusion/Systemic hypersensitivity reactions including anaphylactic reactions	Narrow SMQ “Anaphylactic reaction” Narrow SMQ “Angioedema” Narrow SMQ “Hypersensitivity”
Opportunistic infections	Narrow SMQ “Opportunistic infections”:
Tuberculosis infections	BICMQ Narrow sub-search 8.2 “Tuberculosis related terms”
Malignant tumours	Narrow Sub-SMQ “Malignant tumours” Narrow Sub-SMQ “Haematological malignant tumours” Narrow Sub-SMQ “Non-Haematological malignant tumours”
Malignant skin tumours	Broad Sub-SMQ “Skin malignant tumours”
Skin melanomas	HLT Skin melanomas (excl. Ocular)
Non-melanoma skin cancer (NMSC)	Broad sub-BICMQ “Skin Malignancies excluding melanomas”
Malignancies excluding NMSC	Sub-SMQ “Malignant tumours” excluding broad sub-BICMQ “Skin Malignancies excluding melanomas”
3-point MACE	BICMQ 3-MACE with subsearch 1.1 narrow and subsearch 1.2 narrow *
Torsades de pointes	Broad SMQ “Torsades de pointes/QT prolongation”
Severe infections (according to RCTC grading)	SOC Infections and infestations of at least severe RCTC grade, by HLGT

* this is achieved by retrieving all cases found either by running subsearch 1 in narrow scope (BICMQ search ID 32019093) or subsearch 2 (BICMQ search ID 32019094)

The frequency of patients with AEs will be summarised by treatment, primary system organ class and preferred term. AEs which were considered by the investigator to be drug related will be summarised separately. Separate tables will also be provided for patients with SAEs, patients with AESIs, patients with AE leading to discontinuation of the trial medication, and patients with other significant AEs (as described previously). AEs will also be summarized by maximum intensity.

For disclosure of AE data on ClinicalTrials.gov, the frequency of patients with non-serious AEs occurring with an incidence of greater than 5 % (in preferred terms) will be summarised by treatment, primary system organ class and preferred term. The frequency of patients with SAEs and drug related SAEs will also be summarised respectively.

For disclosure of AE data in the EudraCT register, the frequency of non-serious AEs with an incidence of greater than 5 % (in preferred terms) and the frequency of SAEs will be summarised.

